6.1.1 Clinical Data

Clinical data including summary and demographic data will be collected and entered into a 21 CFR Part 11-compliant data capture system provided by the NCI CCR. Data capture will include baseline and follow up PSA values, testosterone values, use of ADT, presence or absence of biochemical relapse, and questionnaire scores.

Imaging data will include storage of the reconstructed images and image derived parameters on a secure, password protected lab imaging database. Images may also be stored in the clinical center PACS. The lab imaging database will be stored and maintained in the Molecular Imaging Branch facilities. Personal identifiers will not be used when storing imaging data.

NCI Molecular Imaging Branch may exchange anonymized clinical data with working groups, and qualified investigators. The anonymized image data will be stored in an existing secure off-

site imaging database (EXEC PACS) and these images may be shared with researchers at other institutions.

6.1.2 Pre-Administration Events

The presence of any pre-administration event (baseline signs and symptoms present just before 18F-DCFPyL and SBRT administration) will be recorded in a 21 CFR Part 11-compliant data capture system provided by the NCI CCR.

The following information will also be recorded:

- The date and time of evaluation
- The onset time
- The resolution time or duration
- Action taken
- Status of symptom
- Intensity

6.1.3 Imaging Data

Extracted imaging data include:

- (1) PET imaging data will include SUV for each region of interest
- (2) All image data will be stored on a secure server, with access limited to credentialed users. This will permit flexible numeric raw data extraction for quantitative analysis and creation of summary data reports.
- (3) Anonymized image data from this study will be stored in a secure database that is administered by the Cancer Imaging Program, NCI.
- (4) Anonymized image data from this study will be stored in a secure database that is administered by the Cancer Imaging Program, NCI. The data may be shared with research collaborators to improve upon current methods of image analysis. The database is password protected and access is only given to qualifying collaborators.

6.2 DATA SHARING PLANS

6.2.1 Human Data Sharing Plan

What data will be shared?

I will share human data generated in this research for future research as follows (check all that apply):

- Coded and linked data in an NIH-funded or approved public repository.
- Coded, linked data in BTRIS (automatic for activities in the Clinical Center)

How and where will the data be shared?

Data will be shared through:

- An NIH-funded or approved public repository: Clinicaltrials.gov, dbGAP.

- BTRIS (automatic for activities in the Clinical Center).
- Publication and/or public presentations.

When will the data be shared?

- Before publication
- At the time of publication or shortly thereafter.

6.2.2 Genomic Data Sharing Plan

Unlinked genomic data will be deposited in public genomic databases such as dbGAP in compliance with the NIH Genomic Data Sharing Policy.

6.3 RESPONSE CRITERIA

For the purposes of this study, patients should be re-evaluated for response every 1-3 months after treatment with a serum PSA measurement as per the study calendar. Response will be assessed based on PSA.

6.3.1 Definitions

Evaluable for toxicity: All patients will be evaluable for toxicity from the time of their first treatment with SBRT.

Evaluable for response: Only those patients who complete SBRT and have PSA measured after SBRT will be considered evaluable for response. These patients will have their response classified according to the definitions stated below.

6.3.2 Response Criteria

Biochemical control: Biochemical control will be defined using the Phoenix criteria (47). The post-SBRT nadir is the lowest PSA measurement obtained after treatment on this protocol. Biochemical control is defined as a serum PSA less than or equal to 2 ng/dL above the post-SBRT nadir.

Biochemical progression/biochemical failure: Serum PSA more than 2 ng/dL above the post-SBRT nadir. At least 2 PSA measurements separated by 1 month are needed to confirm biochemical failure.

6.3.3 Progression-Free Survival

Biochemical progression free survival (bPFS) will be evaluated on this trial as a secondary endpoint. bPFS is defined as the duration of time from start of treatment to time of PSA progression or death, whichever occurs first. PSA progression (also known as biochemical failure) is defined based on elevation of PSA 2 ng/dL beyond the post-treatment nadir PSA, using the Phoenix criteria (47). A total of 2 PSA values separated by at least 1 month are required to document biochemical recurrence and to reduce the risk of mistakenly classifying a PSA “bounce” as a failure. If the PSA remains elevated, the date of failure will be backdated to the first PSA measurement that exceeded 2 ng/dL above the nadir. Only PSA values collected at the NIH Clinical Center will be used to evaluate disease status given the variability in ranges obtained in different laboratories. Patients who have been treated with androgen deprivation therapy within 3 months before or during this study will not be evaluable for the bPFS endpoint

until their testosterone is within the institutional limit of normal for at least two sequential measurements spaced by 1 month.

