4. PSA failure after definitive radiation as defined by the Phoenix criteria (PSA elevation at least 2 ng/dL above post-radiotherapy nadir). Serial PSA and serial correlative studies will be collected for two years post-treatment.
5. Post-Imaging research and diagnostic biopsies of areas in the prostate identified as suspicious and systematic biopsy. If recent systematic biopsies were obtained (within 5 months) systematic biopsies may not be repeated. Fiducial markers to guide radiation treatment will be implanted simultaneously. If biopsy tissue was obtained within 5 months on another protocol and is available for transfer, biopsy will not be repeated unless clinically indicated. Fiducials will not be implanted again if previously placed and visible.
6. Six months following treatment, patients in both arms will undergo repeat 18F-DCFPyL imaging only if pretreatment imaging was informative.
7. If an 18F-DCFPyL study was performed within 4 months prior to enrollment on a different protocol, it will not be repeated at baseline. In patients treated with androgen deprivation therapy that was initiated within 4 months of a DCFPyL obtained on another protocol, this DCFPyL scan may be used as the baseline scan if the patient remains on ADT and the scan was obtained within 12 months of enrollment.
8. +/- 2 weeks at and after 6 month time point.
9. May be completed by remote visit with a member of the study team (e.g., if the patient is not able to return to the NIH CC). Remote visits will be conducted in compliance with NIH, FDA regulations and local policy. A patient may be referred to their local provider or asked to come to the NIH CC for an in-person assessment, if clinically indicated, and at the discretion of the PI. In the case of any visits with participants' local providers, records will be obtained.
10. Vital signs may be omitted during follow up visits if a patient is unable to return at the NIH clinical center and if the clinical evaluation does not indicate a need for collection.
11. As PSA is a standardized test and the results are comparable across laboratories, if the patient is not able to return to the NIH Clinical center, PSA may be obtained locally. If biochemical failure (PSA elevation at least 2 ng/dL above post-radiotherapy nadir) is identified, the second measurement will be obtained for confirmation per **6.3.2**, ideally at the NIH Clinical Center.

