4 CONCOMITANT MEDICATIONS/MEASURES

Supportive care with blood components, antibiotics, analgesics, and general medical therapy will be provided if the need relates to the performance of protocol assessments (biopsy and imaging procedures) or to treat side effects of therapy. Every effort will be made to refer the patient to their collaborating physician in the community for care unrelated to the protocol therapy or procedures. There are no limitations on the type of non-investigational concurrent medications allowed, as in general, these patients do not receive additional therapy for prostate cancer after radiotherapy, with the exception of hormonal therapy, which will not be delivered on this trial. Concurrent use of androgen deprivation therapy will be allowed but discouraged.

Radiation related side effects will be managed as per the current standard of care without restrictions in medications or procedures that may be performed for management.

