10.3 POPULATIONS FOR ANALYSES

All enrolled patients that initiate treatment with SBRT will be considered evaluable for toxicity. Patients that complete at least one post-treatment PSA will be considered evaluable for biochemical control and biochemical relapse free survival. Patients that complete QoL measures at 3 months will be considered evaluable for these measures. Patients undergoing biopsy following DCFPyL studies will be considered evaluable for the sensitivity and positive predictive value of this study regardless of whether treatment is received.

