10.4.3 Analysis of the Secondary Endpoints

- Define the dose-limiting toxicities and toxicity profile of image-guided, focally dose escalated prostate SBRT in patients previously treated with radiotherapy: DLTs will be reported descriptively.
- Describe the rate of PSA control (bPFS, PSA < 2 ng/dL above post SBRT nadir) at 1 and 2 years after treatment with focally dose escalated SBRT for locally recurrent prostate cancer after irradiation: bPFS will be estimated by the Kaplan-Meier survival analysis and effects of clinical variables on bPFS will be assessed by the Cox proportional hazards model.
- Describe the effects of focally dose escalated prostate SBRT on patient reported outcomes (SHIM, AUA Symptom Index, EPIC-26) in patients previously treated with radiotherapy. The quality of life scores will be summarized at baseline and for each visit. Linear mixed effects model will be used to model quality of life scores at baseline and during and after treatment in which random intercept and random slope are used to account for patient-specific trajectory of quality of life scores. Changes of quality of life scores during and after treatment will be calculated from the estimated linear mixed effect model.
- Evaluate 18F-DCFPyL imaging as a method to detect locally recurrent prostate cancer after radiation. The sensitivity and specificity of DCFPyL for detecting locally recurrent prostate cancer (at baseline) will be reported using biopsy as the gold standard.

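### bPFS runs from the start of SBRT even for men who become evaluable only after testosterone recovery, and 6.3.3 and 10.3 disagree on who is analysed; applied as 6.3.3 reads, 1- and 2-year bPFS can be overstated

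*Combined protocol and SAP*

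**What the plan says.** Section 6.3.3 fixes the time origin and the event: "bPFS is defined as the duration of time from start of treatment to time of PSA progression or death, whichever occurs first". No other origin is given. The same section says of men with ADT in the 3 months before the study, or while on it, that they "will not be evaluable for the bPFS endpoint". The bar is lifted only by recovery, which is described as follows: "until their testosterone is within the institutional limit of normal for at least two sequential measurements spaced by 1 month". There is no limit on the wait.

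Section 10.4.3 names the estimator: "bPFS will be estimated by the Kaplan-Meier survival analysis", with a Cox model for clinical variables. Nothing is said about delayed entry, a landmark, a re-set origin, or how to treat a death or PSA rise before a man becomes evaluable.

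Section 10.3 defines the population differently: "Patients that complete at least one post-treatment PSA will be considered evaluable for biochemical control and biochemical relapse free survival". It has no testosterone condition.

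Such men are foreseen. Section 4 says "Concurrent use of androgen deprivation therapy will be allowed but discouraged", and footnote 7 to the calendar in 3.6 covers men on ADT at enrolment: "this DCFPyL scan may be used as the baseline scan if the patient remains on ADT". Section 6.1.1 lists ADT use and testosterone values among the data captured, but the calendar schedules testosterone only at screening/baseline.

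**The concern.** Suppose a man on ADT becomes evaluable at month 12 and is then timed from SBRT. He contributes 12 months in which, by construction, he could not be an event: had he failed or died in that time, he would not have entered. Ordinary Kaplan-Meier counts him at risk throughout, which enlarges the early risk sets without adding early events. This is left truncation handled as if all men had been observed from time zero.

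At stake are the 1- and 2-year bPFS rates, a secondary endpoint that 10.1 expects to compare favourably with 75% from brachytherapy series. Settling when testosterone is drawn, or which PSA is the nadir, would not by itself repair the risk set.

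**Working it through.** The plan states no precision, event count or power for bPFS, so there is no figure of its own to reproduce.

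**Inputs from the documents.** Benchmark 75% (10.1), used here as an illustrative true 2-year rate; follow-up of 24 months (3.5, 3.6); at most 42 evaluable men (10.2).

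**Assumptions, not in the documents.** A constant hazard, a late-evaluable share a, and a time to evaluability E spread evenly over 0.5 to 1.25 years.

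**Step 1, the true curve.** λ = −ln(0.75)/2 = 0.1438 per year. S(1) = exp(−0.1438) = 86.6%; S(2) = 75.0%.

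**Step 2, ordinary Kaplan-Meier when events before recovery are left out.** With a as the share of analysed men, the method estimates

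(1 − a)·exp(−λt) + a·mean[exp(−λ·max(0, t − E))].

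The mean term is 0.977 at 1 year and 0.851 at 2 years.

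- a = 30%: 0.7 × 0.866 + 0.3 × 0.977 = 89.9% at 1 year; 0.7 × 0.750 + 0.3 × 0.851 = 78.0% at 2 years. Excess 3.3 and 3.0 points.
- a = 15%: 88.3% and 76.5%. Excess 1.7 and 1.5 points.
- a = 5%: 87.2% and 75.5%. Excess about 0.5 points at each time.

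**Step 3, a wider grid.** With a fixed recovery time d, and the ADT share taken among treated men, the 2-year excess runs from 0.3 points (10% share, d = 3 months) to 8.1 points (50% share, d = 18 months). If true 2-year bPFS is 82%, the rate quoted in 1.2.1 for the earlier SBRT series, the same grid gives 0.2 to 6.1 points.

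**Step 4, dependence on how events before recovery are handled.** Simulations with 42 men, 30% of treated men on ADT and evaluability at 6 to 15 months; results agree between runs to a few tenths of a point. The truth is 86.6% / 75.0%.

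| Handling | Ordinary KM, 1 / 2 years | Delayed entry, 1 / 2 years |
|---|---|---|
| Left out | 89.6% / 77.7% | about 86.6% / 75.0% |
| Counted at their true dates | 86.6% / 75.1% | not needed |
| Masked, surfacing within 3 months after recovery | 88.4% / 74.9% | 84.8% / 71.7% |
| Men without ADT only | 86.5% / 75.1% | not needed |

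**Step 5, the nadir.** Section 6.3.2 takes the lowest PSA after SBRT and does not exclude values under ADT. A rise on testosterone recovery could then be scored as failure. For recovery at d months, the share of late-evaluable men with a false failure that would cancel the 2-year excess is 1 − S(24)/S(24 − d) = 1 − 0.75^(d/24). That is 3.5% at d = 3 and 19% at d = 18.

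**The case against.** The strongest reply is that the decisive step is implied rather than written. Being not evaluable until recovery can be read as joining the risk set at recovery, which is delayed entry. Section 10.3 would put ADT-exposed men at risk from SBRT with their early events counted, and then there is no truncation. Section 6.3.3 also backdates a confirmed failure to the first PSA above the threshold; if that reaches back before recovery, the PSA part of the bias disappears. All of this stands. It shows that the rule is open, not that it is settled: no passage states risk-set entry or says whether backdating covers PSA values taken before recovery, and 10.3 contradicts 6.3.3 rather than explaining it.

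Three stronger conclusions are tempting, and the documents do not support them.

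- A reader might infer that bPFS is always raised. That holds for this mechanism alone; a suppressed nadir, or failures that surface after recovery, can offset it.
- A reader might infer that ADT will look protective in the Cox model. Section 10.4.3 mentions only clinical variables and does not name ADT, and no Cox effect was computed.
- A reader might infer that delayed entry alone is the cure. If ADT masks failures that then surface, ordinary Kaplan-Meier is about right at 2 years, while delayed entry reads about 3 points low.

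The objection on size is also fair. Section 4 discourages concurrent ADT and says that hormonal therapy is not delivered on the trial, so the share may be small. The standard error at 42 men is √(0.75 × 0.25/42) = 6.7 points. The endpoint is descriptive, with no test or decision rule. And without follow-up testosterone values, few ADT-exposed men may ever meet the condition in 6.3.3.

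**Conclusion.** The point holds in a limited form. Sections 6.3.3 and 10.3 conflict on who is evaluable, and the plan does not say when ADT-exposed men enter the risk set or what becomes of their earlier events. Applied as 6.3.3 is written, with men who fail or die before recovery left out, ordinary Kaplan-Meier from SBRT overstates 1- and 2-year bPFS. The excess is about 0.5 points at a 5% share and about 3 points at 30%, with recovery at 6 to 15 months, a constant hazard and a true 2-year rate of 75%.

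The shares, recovery times and hazard shape are assumptions. The net direction in the actual data cannot be told from the documents. The excess is smaller than the sampling error, but it is systematic, bears on the comparison with 75%, and can be avoided by wording.

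**What to change.** 1. Make 10.3 and 6.3.3 give one definition of evaluability for bPFS.
2. Name, as the estimate to be set against 75%, the 1- and 2-year bPFS in men with no ADT within 3 months before or during the study. It avoids this problem and uses ADT data that 6.1.1 already captures.
3. Beside it, report an all-patient estimate with time still measured from SBRT and ADT-exposed men entering the Kaplan-Meier and Cox risk sets at their second normal testosterone. Give numbers at risk by time. State how deaths and PSA failures before entry are treated, and note that this estimate can read low if ADT masks failures that appear after recovery.
4. Collect follow-up testosterone dates for ADT-exposed men, since the entry date depends on them and the calendar does not schedule them.

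Cost: SAP wording, an entry-time variable, the extra testosterone dates, and fewer men in the main estimate. If 30% were excluded, 42 × 0.7 = 29.4 men would remain and the standard error would rise from 6.7 to √(0.75 × 0.25/29.4) = 8.0 points. The reported bPFS may also be less favourable.

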3.6 STUDY CALENDAR

| Procedure | Screening/ Baseline | Active SBRT treatment | Post Therapy Follow-up (1, 3 mos) 15 | Post Therapy Follow-up 6 months post-SBRT | Post Therapy Follow-up (9 mos and q 3 mos until 24 mos) 8 | |
|--|------------------------|-----------------------------|---|--|---|--|
| History and PE | X | | | | | |
| Vital signs 10 | X | | X | X | X | |
| Performance Score | X | | | | | |
| Weight | X | | | | | |
| Labs | | | | | | |
| CBC, Acute care panel, LFTs, Testosterone, PT/PTT, Viral serologies 2 | X | | | | | |
| PSA 4 | X | | X 11 | X 11 | X 11 | |
| Biopsies (ultrasound guided)/fiducials 5 | X | | | | | |
| mpMRI 3 | X 3 | | | X 12 | | |
| 18F-DCFPyL PET/CT imaging | X 7 | | | X 6, 12 | | |
| 18F-NaF PET/CT imaging 3 | X | | | | | |
| Whole body bone scan 3 | X | | | | | |
| Clinical evaluation | | X | X 9 | X 9 | X 9 | |
| Adverse Events | X | | Monitored continuously | | | |
| Concomitant Medications | X | | Monitored continuously | | | |
| Correlatives | | | | | | |
| Research Biopsy 5 | X | | | | | |
| Blood 12 | X | X 1 | X | X | X | |
| Urine 12 | X | | X | X | X | |
| Questionnaires | | | | | | |
| EPIC-26, SHIM, AUA-SI, DRS, PROMIS 13, 14 | X | | X | X | X | |

1. Correlative blood sampling should be performed within 24 hours after the last dose of irradiation.
2. CBC with differential, chemistries (to include creatinine BUN, PSA, testosterone, Alk Phos, ALT, AST, Bilirubin), PT, PTT within 4 weeks of study entry. Viral serologies: HIV, Hepatitis B, and Hepatitis C screening within 4 weeks of study entry. Acute Care Panel: (Sodium (NA), Potassium (K), Chloride (CL) Total CO₂ (Bicarbonate), Creatinine, Glucose, Urea nitrogen, eGFR).
3. Whole body bone scan, F18 NaF PET, and multiparametric MRI of the prostate. In selected patients, a CT of the abdomen and pelvis (with oral and IV contrast) may also be obtained for staging, particularly if MRI is not felt to adequately have staged the pelvic and abdominal lymph nodes. All imaging studies should be completed within 3 months prior to study entry. MRI of the prostate obtained more than 3 months (no greater than 5 months prior to entry) may be used if a biopsy has recently been performed, as post-biopsy MRI may not be easily interpretable due to hemorrhage.

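### Section 6.3.3 judges biochemical failure on NIH PSA values only, while calendar footnote 11 accepts local PSA; the bPFS population and the handling of ADT also need one stated rule

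*Combined protocol and SAP*

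**What the plan says.** **PSA source.** Section 6.3.3 (Progression-Free Survival) says "Only PSA values collected at the NIH Clinical Center will be used to evaluate disease status" and gives variation between laboratories as the reason. Section 3.6 (Study Calendar), footnote 11, says "As PSA is a standardized test and the results are comparable across laboratories" and continues "if the patient is not able to return to the NIH Clinical center, PSA may be obtained locally". If failure is identified, the second value is to be taken "ideally at the NIH Clinical Center". The calendar row reads "PSA 4 | X | | X 11 | X 11 | X 11", so footnote 11 applies to every follow-up PSA. On dating, 6.3.3 says that "the date of failure will be backdated to the first PSA measurement that exceeded 2 ng/dL above the nadir". Section 6.3.2 defines the nadir as the lowest post-treatment PSA and does not say which laboratory's values qualify.

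**Population.** Section 6.3.1: "Only those patients who complete SBRT and have PSA measured after SBRT will be considered evaluable for response". Section 10.3: "Patients that complete at least one post-treatment PSA will be considered evaluable for biochemical control and biochemical relapse free survival".

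**ADT.** Section 4 allows concurrent ADT but discourages it. Section 6.3.3 makes patients with ADT in the 3 months before the study, or during it, non-evaluable for bPFS until two sequential testosterone values a month apart are normal. The calendar marks testosterone at screening/baseline only, although 6.1.1 lists testosterone and ADT use among the data captured. Section 10.4.3 names Kaplan-Meier and Cox and gives no censoring rule.

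**The concern.** Two analysts, each following a section of the protocol faithfully, could report different 1- and 2-year bPFS from the same patients. They could differ in which PSA values set the nadir, which value is the first crossing, and whether a local second value confirms failure. Because failure is backdated to the first crossing, the choice of laboratory rule also sets the event date.

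The handling of ADT raises a separate question of bias. Where ADT is started because PSA is rising, taking the patient out of the analysis before the second PSA removes a probable failure. A failure already confirmed before ADT is not exposed to this.

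bPFS is the trial's main efficacy description and is set informally against a 75% brachytherapy rate in section 10.1. It is a secondary, descriptive endpoint with no test attached.

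**Working it through.** The plan states no figure that depends on these rules, so there is nothing to reproduce. The check compares the texts and then gauges size under labelled assumptions.

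**1. One patient under both rules.** Take a local PSA above the threshold at month 12 and an NIH value, still above it, at month 13.
- Footnote 11: the local value identifies failure, the NIH value confirms it, and failure is backdated to month 12.
- Section 6.3.3, NIH values only: the first crossing is month 13 and needs a further NIH value. The patient is event-free at 1 year.

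Each such patient moves 1-year bPFS by 1/42 = 2.4 points, or 1/21 = 4.8 points within one arm. These are the maximum evaluable numbers in section 10.2, which the plan itself calls likely over-estimated.

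**2. Size of the PSA-source effect.** The documents do not give the share of local visits, so it is assumed.

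*Simple model.* Exponential failure with 75% event-free at month 24; visits at months 1, 3, 6, then every 3 months; each visit local with probability p; an NIH value always obtained one month after a local crossing. Only crossings first seen at the landmark visit shift past it:
- 1 year: p × (0.75^(9/24) − 0.75^(12/24)) = p × (0.8977 − 0.8660) = p × 0.0317. This gives 0.3 points at p = 10% and 0.8 at 25%.
- 2 years: p × (0.75^(21/24) − 0.75) = p × 0.0275. This gives 0.3 and 0.7 points.

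If the extra NIH value is obtained only half the time, simulation gives +0.3 and +0.9 at 1 year and +0.3 and +0.8 at 2 years. If event-free patients are instead censored at their last NIH value, the 2-year change is 0.0 at 10% local and −0.3 to −0.4 at 25%.

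*Fuller model.* This adds a running NIH-only nadir and a confirmatory value, using assumed PSA curves that are not in the documents.

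| Local visits | 1 year | 2 years, followed to month 24 | 2 years, censored at last NIH value |
|---|---|---|---|
| 10% | +0.6 to +0.7 | +0.1 | −0.1 |
| 25% | +1.7 to +1.9 | +0.2 to +0.4 | −0.5 to −0.6 |

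Across both models, the 1-year shift is +0.3 to +1.9 points and the 2-year shift −0.6 to +0.8. At 50% local visits the ranges widen to +1.4 to +4.5 and −3.7 to +2.1. That share is less plausible, since section 10.2 expects patients mainly from the local area.

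**3. ADT started for a rising PSA.** Assume 42 patients and 10 failures, of whom k start ADT at an unconfirmed crossing.
- Counted as events: 32/42 = 76.2%.
- Removed: 32/(42 − k) = 78.0, 80.0 and 82.1% for k = 1, 2, 3.
- Censored at ADT start: the product of (1 − 1/n) over the remaining failures, averaged over which k are censored. For k = 1 this runs from 32/41 = 78.0% (earliest crossing censored) to 33/42 = 78.6% (latest), average 78.3%. For k = 2 and 3 the averages are 80.4% and 82.7%.

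Censoring alone therefore shifts the estimate as much as removal does.

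**4. ADT unrelated to failure.** Assume true 2-year bPFS of 75%, exponential times, and a proportion q starting ADT by month 24. With f = −ln 0.75 and a = −ln(1 − q), failures before ADT are e = f/(f + a) × [1 − 0.75(1 − q)]. After removing patients who start ADT before failure, the estimate is 0.75(1 − q)/[0.75(1 − q) + e]. For q = 10%: e = 0.732 × 0.325 = 0.238, and 0.675/0.913 = 73.9%. For q = 20% and 30% the results are 72.7% and 71.2%. Removal now biases downward; censoring does not bias.

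**5. Testosterone.** Follow-up visits are at months 1, 3, 6, 9 and every 3 months to 24, so PSA draws are 2 to 3 months apart. Adding testosterone to them would not meet a literal one-month spacing.

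**6. Precision for scale.** The exact (Clopper-Pearson) 95% interval for 32/42 is 60.5–87.9%.

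**The case against.** The strongest reply is that footnote 11 governs where blood may be drawn and 6.3.3 governs which values are analysed. On that reading local monitoring with NIH-only analysis is possible, and a reader who inferred that the two rules cannot both be followed would go too far. That much stands. It does not dissolve the conflict, because footnote 11 also covers identifying and confirming failure, and the two sections give opposite reasons. Nor should one infer that many patients would lack any NIH value: month-6 MRI is scheduled, and footnote 12 says delayed imaging will still be completed.

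A reader might also infer three incompatible bPFS populations. The text does not support that. The ADT condition in 6.3.3 can be layered on 10.3 as a temporary suspension, and 6.3.1 speaks of response, although section 6.3 bases response on PSA. The real difference is whether SBRT must be completed. It should touch few patients: treatment is five fractions over 7–14 days (3.8.4) and no drop-out is anticipated (10.2).

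The plan is not silent on ADT either, since 6.3.3 expressly covers ADT during the study. What it leaves open is how that suspension enters the Kaplan-Meier estimate.

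**Conclusion.** The PSA-source conflict between 6.3.3 and footnote 11 is real and should be fixed. It changes which values count and when failure is dated. At 10–25% local visits, the NIH-only rule raises 1-year bPFS by about 0.3 to 1.9 points and moves 2-year bPFS by less than 1 point in either direction. These sizes rest on assumed visit shares and PSA behaviour, and they are small beside the sampling uncertainty.

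The population and ADT points are secondary. With 1 to 3 of 42 patients starting ADT for a rising PSA, bPFS would read about 78–83% instead of 76.2%. The number of such patients is an assumption, and section 4 discourages ADT. It would be tempting to say that the ADT rule always inflates bPFS. It does not: the direction depends on why ADT was started and on whether patients are removed or censored.

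Nothing here touches the MTD. Delayed entry, and the nadir rule for patients already on ADT at entry, are optional clarifications rather than errors.

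**What to change.** - **PSA source.** Reconcile 6.3.3 with footnote 11 in one rule covering nadir, first crossing and confirmation. Use all protocol PSA values in the main analysis and NIH-only values in a sensitivity analysis. This uses data the calendar already allows; the price is some between-laboratory variation.
- **Population.** State one bPFS population in the same words in 6.3.1, 6.3.3 and 10.3, including whether completed SBRT is required.
- **ADT started after SBRT.** Do not remove these patients. Report bPFS censored at ADT start and, beside it, bPFS with ADT started for a rising PSA counted as an event. Say explicitly that this replaces the 6.3.3 suspension for them. The cost is two figures instead of one, and a PSA bounce may be counted as failure in the second.
- **Testosterone.** Reconcile the 6.3.3 condition with the calendar, for example by asking for two consecutive normal values at least 1 month apart and adding the assay at existing visits for ADT-exposed patients. Keeping the literal one-month spacing would need extra draws.

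The cost is mainly wording, plus a few assays, some of which may have to be run locally. Settle the rules before the bPFS analysis and report how many patients each one affects.
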